5.4 Duration of Study

Active participation by a given subject will be complete approximately 6 months after cycles 1, 2, 3, and 4 based on participants' treatment schedule. Ongoing data collection through medical record abstraction will continue for collection of use of UNC services.

5.5 Abstraction of Medical Records and Patient Follow-up Contact

Data abstraction will occur periodically throughout the duration of the study at least weekly.

Variables that will be extracted from the medical records for each patient include, but are not limited to: age, gender, race, ethnicity, diagnosis, education level, type and amount of prior cancer treatment, medical comorbidities and medications, type/dose/date of AML treatment, days hospitalized during cancer treatment (including outside hospitalization if directly transferred to UNC from another facility), subsequent hospitalizations, date of death (if appropriate), electronic notes of occupational and physical therapy, blood test results (such as white blood cell count, Absolute neutrophil count, hemoglobin, platelet, lactate dehydrogenase, C-Reactive Protein), and remission status.

6.0 ASSESSMENT OF SAFETY

Safety will be monitored in all patients from the time of enrollment.

7.0 ASSESSMENT OF EFFICACY

Patients with absolute contraindications to activity monitoring including bilateral lower extremity amputation, unilateral lower extremity amputation without prosthesis and unstable angina or myocardial infarction during the previous month will not be excluded from the study. These patients, therefore, will not be included in any analyses requiring these measures.

8.0 TIME AND EVENTS TABLE

Table 5. Measures

Variable Measured	Measure Description and Reliability	Baseline cycles 1 & 2 (7 days prior or within 3 days of infusion initiation)	Symptom and QOL BOTH GROUPS (About days 1-60)	HMA or low-dose cytarabine completion at cycle 1 & 2 (within 2 days or up to 7 days after the end of infusion)	Post-discharge, 2x week assessments Monday & Thursday INTERVENTION ONLY days 8-30	Before cycle 4 (About day 90)	Data Collector
Demographic and clinical variables	Age, sex, race/ethnicity, insurance, education, income, employment status, marital/partner status, number of people in the household. Treatment type, comorbidities, remission status, blood test results, height and weight.	X			Continuously monitor clinical characteristic, ex: blood result, remission status		Research Assistant
Health Care Utilization	Number and reasons for: emergency department visits, rehospitalizations Length of hospital			Electronic chart abstraction and self-report			Research Assistant
Quality of Life							
QOL	EORTC QLQ-C30 ³⁰ , $\alpha = .89$ (5 functional scales, global health status/QOL scale, cognition, financial impact)	X	X (baseline of cycle 3)			X	Research Assistant
Symptoms							
AML symptoms	PRO-CTCAE 19 items ⁴² (diarrhea, chills, heartburn, nausea, appetite, mouth sores, vomiting, constipation, cough, rash, shortness of breath, fatigue, anxiety, sadness*, nothing will cheer me up, pain, insomnia, concentration, and memory)	X	X	X	X	X	PACT RN
Disease burden	FACT-Leu Additional Concern subscale	X				X	Research Assistant
Function							
Participation in Meaningful Activity	Possibilities for Activity Scale (PActS) ³⁴ - 12 items stratified $\alpha = .77$ – internal consistency .91 - .89	X				X	Research Assistant
Performance Status	Clinician reported Karnofsky Performance Scale ³⁷ - 1 item for clinician; $r = .89$	X		X		X	Research Assistant
Self-care	PASS- Performance Rate Assessment of Self-Care Skills	X					PACT OT
Grip Strength	Hand grip strength	X					PACT OT
Balance	Berg balance test	X					PACT PT
Mobility	Timed Up and Go (3 meter)	X					PACT PT
Function	Activity Measure for Post-Acute Care (AM-PAC) "6 clicks" - 6 items for OT; 6 items for PT; $\alpha = .92 - .94$	X					PACT OT and PT
Cognition abilities	Clock Drawing Assessment	X					PACT OT
Readiness for Discharge and Self-Management							
Readiness for Discharge	Care Transitions Measure ⁴³ , 15 items, $\alpha = .93$			X			PACT RN
Self-management	Patient Activation Measure ⁴⁴ , 13 items, $\alpha = .87$			X			PACT RN
Preparedness for Caregiving	Preparedness for Caregiving Scale			X			PACT RN
Other							
Patient and Caregiver Interview				X			Research Assistant

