1.3 Symptom Management Intervention

The proposed symptom management intervention, PACT, utilizes a collaborative, multidisciplinary, integrated team including RNs, OTs and PTs. The PACT intervention is unique in its interdisciplinary approach and was designed to facilitate the integration among the team to plan, implement and evaluate outcomes.

The RN, OT and PT will use the Adaptive Leadership Framework for Chronic Illness⁸ as a guide for the intervention.

1. The RN will complete a symptom assessment within 2 days of patient admission and will continue to monitor the patient's symptoms daily throughout hospitalization. OT and PT project staff will assess and monitor function and physical health status within 2 days of patient admission and will continue to monitor the patient's symptoms at baseline, day 4 and at discharge.
2. Collaborating with the patient, RN, OT, and PT will identify and monitor symptoms of AML treatment-related and chronic illness symptoms that might interfere with the patient's ability to engage in functional and physical activities, such as dressing, grooming, or walking and getting out of bed.
3. The RN, OT, and PT will meet with the patient to exchange information and develop a shared understanding, defined by acknowledgement of symptoms and treatment related challenges and an agreed-upon plan for each OT and PT visit. Shared understanding will be determined by evaluating electronic notes and consensus between the RN, PT, and OT.
4. This shared understanding becomes the basis for developing a plan of care jointly that will be reviewed and updated as the patient's symptoms, functional level and/or physical health changes. *For example, if the patient shares with the RN, OT, and PT that he/she is experiencing fatigue (an adaptive challenge), then the RN, OT, and PT will add to the shared meaning by explaining the essential need for movement to increase the patient's ability to engage in functional and physical health activities to reduce fatigue. The joint plan will define shared meaning across team members with the patient.*
5. The RN, OT, and PT will address technical challenges, *for example, if a patient has difficulty sleeping, RN can address medication administration, the OT can provide*

strategies for sleep hygiene and address fatigue, and the PT can address staying active during hospitalization to maintain physical health needed for improved sleep.

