2.0 STUDY PURPOSE AND DESIGN

This is a single institution, feasibility trial of 20 (10 control and 10 intervention) patients with the primary objective of assessing feasibility, acceptability, and change in pre and post measures of symptoms, function, and QOL by administering the PACT intervention.

Study subjects will be identified by the Study Coordinator through pre-screening through the electronic health record after being referred by the oncologists and pharmacists. Eligible patients will be approached by the Study Coordinator to confirm eligibility, which includes requesting permission of the patient's attending physician. Seven days prior to and within three days after initiation 1st cycle HMA or low-dose cytarabine + VENE, written informed consent will be obtained (A total of 10 days of recruitment period and baseline assessment).

First, ten participants in the control group will receive usual care. After the control patients have completed the study, then 10 intervention participants will receive the PACT intervention, a novel symptom management intervention, which aims to build patient skills to manage AML treatment-related, and chronic illness symptoms. Because patients receive chemotherapy during the first 7 days of hospitalization or clinic visit, the intervention will start at day 1 or day 2 of chemotherapy. During hospitalization, the PACT RN will assess AML symptoms daily (using PRO-CTCAE), and PACT OT and PT will assess function at baseline (day 1 or 2), days 3 or 4, and days 6 or 7. This study uses UNC hired staff of RNs, OTs, and PTs to deliver the intervention.

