5.2 Study Assessments

At the time of baseline assessment, patients with no contraindications to activity will undergo quality of life, symptom, OT and PT assessments, as well as medical chart abstraction.

At follow up time points, participants will complete the assessments and questionnaires per the Time and Events table (see section 8.0). We have completed daily and weekly measures with adults undergoing a hematopoietic transplant^{26,27} and those with acute leukemia during their hospitalization.^{28,29} Patients are able to complete daily assessments within 5 minutes.

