Analyses will be conducted following an intention to treat approach, such that patients are analyzed as allocated. Descriptive statistics will be computed on all analysis variables at each time point separately for each condition. These values will be compared between the conditions at baseline to determine whether any imbalanced. These include means and standard deviations for continuous variables, and frequencies and percentages for categorical variables. As the primary analysis of pre and post values, we will fit an analysis of covariance (ANCOVA) model for each post outcome, with a main effect for group (intervention versus control) while controlling for the covariate of the corresponding baseline (pre) value. Sensitivity analyses will repeat this ANCOVA but adding demographic variables that are imbalanced at baseline, subject to sufficient sample size. This approach will allow us to assess whether the mean post values differ between groups for each measure through the regression coefficient for the main effect of group, as well as its 95% confidence interval. This information will be useful in planning for the subsequent R01, and we will calculate effect sizes for the post measure as the ratio of the mean difference between the intervention and the control groups to its standard deviation. For measures where more than one follow-up measure is collected, this approach can be extended through a linear mixed effects model approach to repeated measures analysis, and within-patient correlation can be estimated. If extensive (e.g., greater than 10%), multiple imputation will be considered for missing values. No formal significance testing will occur, as the intention is to evaluate and estimate effect sizes rather than formal hypothesis testing, and hence multiplicity is not a concern from this perspective.

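### Table 5 schedules the six OT/PT-administered tests only at the cycle 1 and cycle 2 baselines, so the last value falls at about day 31, midway through PACT, and conflicts with the text and with the planned pre/post comparison

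*Combined protocol and SAP*

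**What the plan says.** Section 3.1 puts change in function, compared between control and intervention patients, within the primary objective. Section 10.3 states the analysis: "we will fit an analysis of covariance (ANCOVA) model for each post outcome", with group as the main effect and the matching baseline value as covariate.

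Section 5.2 makes Table 5 the schedule: at follow-up, "participants will complete the assessments and questionnaires per the Time and Events table (see section 8.0"). In that table the row "Timed Up and Go (3 meter") has one mark, in the column "Baseline cycles 1 & 2 (7 days prior or within 3 days of infusion initiation"). PASS, grip strength, Berg, AM-PAC and clock drawing show the same pattern. The nearby row "Clinician reported Karnofsky Performance Scale" also has marks at infusion completion and before cycle 4.

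The text gives other times. Section 2.0 says that during hospitalization "PACT OT and PT will assess function at baseline (day 1 or 2), days 3 or 4, and days 6 or 7". Section 1.3 has OT and PT assess function and physical health within 2 days of admission and then keep monitoring "at baseline, day 4 and at discharge". Section 5.1 says that all patients, in either group, receive an identical set of quality of life, symptom and functional measures at baseline and at later time points, and refers to the timeline for the details.

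**The concern.** A pre/post comparison needs a post value, taken at a stated time in both groups. For the six tests Table 5 offers only a second baseline, and section 10.3 does not say which value counts as post. Because the table calls the cycle 2 assessment a baseline, an analyst could take it as an outcome or as a covariate.

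At stake is the estimated effect of PACT on mobility, balance, strength, self-care and clinician-rated function. These are the domains that the OT and PT components target, and section 10.3 intends the effect sizes for planning the next study. Under section 2.0 the ten controls complete the study before the intervention patients begin. A test missed in controls because the schedule was unclear cannot be recovered later.

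**Working it through.** The plan gives no figure for this point, so the check is to read Table 5 by column, date the columns, and compare them with the text.

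**Marks in Table 5**

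| Measure | Baseline, cycles 1 and 2 | Days 1–60 | Infusion completion, cycles 1 and 2 | Post-discharge (intervention only) | Before cycle 4 |
|---|---|---|---|---|---|
| PASS, grip, Berg, Timed Up and Go, AM-PAC, clock drawing (six rows) | X | – | – | – | – |
| KPS | X | – | X | – | X |
| PActS | X | – | – | – | X |
| QLQ-C30 | X | X (cycle 3 baseline) | – | – | X |

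The Function block has eight rows: the six tests, KPS and PActS. Six of the eight have no mark after the baseline column. QLQ-C30 sits under Quality of Life, but section 5.3.1 says it includes five functional scales, among them physical and role function.

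**Timing inputs.** Cycle 2 infusion runs on days 31–37 and cycles last 30 days (section 1.2). PACT covers cycles 1 and 2, about 60 days (section 1.1). The baseline window is 7 days before to 3 days after infusion starts (Table 5).

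- Cycle 2 baseline window: 31 − 7 = day 24, to 31 + 3 = day 34.
- PACT remaining after a day-31 test: 60 − 31 = 29 days. Across the window this is 60 − 34 = 26 to 60 − 24 = 36 days.
- Last check under section 2.0: day 6 or 7. If the pattern repeats in cycle 2, which is an assumption, it is 30 + 6 = day 36 or 30 + 7 = day 37.
- Completion column, "HMA or low-dose cytarabine completion at cycle 1 & 2 (within 2 days or up to 7 days after the end of infusion"): for cycle 2, about day 37 to 37 + 7 = day 44.
- Cycle 3 baseline: 2 × 30 + 1 = about day 61.

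**Comparison.** Table 5 places the six tests at about days 1 and 31. Section 2.0 places OT/PT function checks within days 1–7, and section 1.3 at baseline, day 4 and discharge. Neither section names the instruments. No section gives a value for the six tests near day 60 or day 90.

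Table 1 schedules OT and PT contact on days 1–7 and 31–37 and only nurse calls on days 38–60. A test at cycle 2 infusion completion would therefore fall at the end of OT/PT contact, with 60 − 44 = 16 to 60 − 37 = 23 days of nurse calls still to come.

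**The case against.** Four arguments on the other side deserve weight.

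**The comparison is not impossible.** A reader might infer that the six tests are done once and that no ANCOVA can be fitted. The documents do not support that. The column covers two baselines, and section 10.3 never defines post as the end of PACT. A model with the cycle 2 value as outcome and the cycle 1 value as covariate can be fitted, but it estimates a mid-intervention contrast that the plan does not name.

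**Controls may well be tested.** A reader might infer that the days 3–4 and 6–7 checks are for intervention patients only, because section 2.0 speaks of PACT OT and PT. That is not established. Table 5 lists PACT OT and PT as collectors of the baseline tests, and a PACT RN as collector of PRO-CTCAE, which both groups answer. Section 5.1 points towards both groups. Later testing of controls is nevertheless not clearly stated, and Table 5 shows none.

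**The table may have been damaged when it was read from PDF.** Some entries, such as the continuous monitoring of clinical characteristics, look like spanning cells collapsed into one column. This cannot be excluded. However, KPS, PActS and the Care Transitions Measure kept their marks in later columns, so loss in exactly these six rows is unlikely. Section 3.5 is redacted and may bear on these outcomes.

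**The consequences are limited.** The decision rule in section 10.2 uses recruitment and retention only, and section 3.4 lists feasibility and adherence as endpoints. Function is estimated without formal testing, in a study whose stated half-width for QOL is .9SD with 10 per group. This stands and limits the severity. The 75% data-collection target in section 3.1 is affected slightly, because its denominator depends on which visits are intended.

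**Conclusion.** The schedule and the text disagree. Followed as written, Table 5 leaves six of the eight Function rows with a last value at about day 31 of roughly 60, and their post time point is undefined.

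The gap does not extend to all measures of function. KPS has values at infusion completion and about day 90, PActS at about day 90, and the QLQ-C30 functional scales at the cycle 3 baseline and about day 90. A reader might infer that only KPS and PActS remain, or that these two supply a day-60 value. The first inference overlooks QLQ-C30. The second fails because neither has a day-60 mark, and the nearest to the end of PACT is QLQ-C30 at about day 61.

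The conclusion assumes that the table marks were read correctly and that cycles follow the 30-day pattern in section 1.2. It should be fixed because it determines whether part of the stated objective can be estimated at an interpretable time. It does not undermine the feasibility decision.

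**What to change.** Reconcile sections 1.3, 2.0, 5.1 and Table 5:

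1. In Table 5, mark the six tests in the infusion-completion column for cycles 1 and 2, for both groups.
2. In sections 1.3 and 2.0, name the instruments used at each OT/PT check, say whether controls have them, and align the days with the table.
3. In section 10.3, name the cycle 2 completion value (about days 37–44) as the post value for these tests and the cycle 1 baseline as the covariate. Describe the result as the contrast at the end of OT/PT contact, not at the end of PACT. An end-of-PACT contrast would need a further test near day 60.
4. If controls will not be tested at completion, limit the stated function comparison to KPS, PActS and the QLQ-C30 functional scales.

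The cost is an amendment to one table and a few sentences, plus some therapist time in controls. Section 2.0 already plans visits on days 6 or 7, and section 5.1 already promises controls the same battery. The change is most useful before control testing is under way, because missed control values cannot be recovered.

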The first 10 patients will be assigned to the control group. All patients (assigned to either intervention or control groups) will undergo the exact same battery of quality of life, symptom, and functional measures at baseline (prior to beginning the intervention), and throughout different time points throughout the study (see Data Collection Procedures/timeline below). Once consent is provided, study personnel may contact enrolled participants up to 2 years from their acute leukemia diagnosis. All patients cluster randomized into the intervention group will receive standard care plus the PACT intervention for the duration of the study.

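### Patient activation and caregiver preparedness have no pre-PACT value, so a difference between the two consecutive groups cannot be adjusted for prior levels and change cannot be estimated

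*Combined protocol and SAP*

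**What the plan says.** Table 5 in Section 8.0 has a block for readiness for discharge and self-management. In it the "Patient Activation Measure" (13 items) and the "Preparedness for Caregiving Scale" are each marked once, in the column headed "HMA or low-dose cytarabine completion at cycle 1 & 2 (within 2 days or up to 7 days after the end of infusion". Their baseline cells are empty, and no other section schedules either measure at baseline.

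Section 2.0 says that "the intervention will start at day 1 or day 2 of chemotherapy".

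Allocation is by order of enrolment. Section 5.1 states "The first 10 patients will be assigned to the control group", and Section 2.0 adds "After the control patients have completed the study, then 10 intervention participants will receive the PACT intervention".

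Section 10.3 says "we will fit an analysis of covariance (ANCOVA) model for each post outcome", with a group effect and "controlling for the covariate of the corresponding baseline (pre) value". The sub-heading over that text names quality of life, symptoms and function. Sensitivity analyses add demographic variables that are imbalanced at baseline. No other between-group model is given.

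**The concern.** Section 5.3 describes the activation measure as assessing self-management, and Sections 1.6 and 1.7 present patient self-management as what PACT works through. It is therefore a natural place to look for an early signal. Caregiver preparedness is not described as a PACT mechanism, but it is collected in both groups and will be compared.

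Without a pre-PACT value, a difference at infusion completion may reflect PACT, or it may reflect how activated or prepared the later patients and caregivers already were. Randomisation would balance such differences on average, but enrolling one group after the other does not. The results are meant to inform a larger study, and for these two measures the plan can supply neither an estimate of change nor a pre/post correlation.

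**Working it through.** **1. Timing.** PACT starts on day 1 or 2 of chemotherapy, and Table 1 (Section 1.5) has daily nurse contact on days 1-7. The first activation and preparedness values come at the end of the cycle 1 infusion, so in the PACT group they follow up to about a week of PACT. The cycle 1 value cannot stand in as a baseline for cycle 2. The Karnofsky row of Table 5, marked at baseline, infusion completion and before cycle 4, fits this reading of the columns.

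**2. Can the measures be taken earlier?** The Care Transitions items (Section 13.2.14) ask about a hospital stay and discharge that have already happened, so they can only be asked afterwards. The activation items (13.2.15) ask about general confidence, knowledge and habits. The caregiver form (13.2.16) asks for answers even about care not yet being given. Both can be completed at enrolment.

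**3. Which analysis applies?** There are two readings of 10.3:
- If its wording on every post outcome covers these measures, the model needs a covariate that is not collected and cannot be fitted to them.
- If the sub-heading limits the ANCOVA to quality of life, symptoms and function, these measures have descriptive statistics but no named between-group model.

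Either way 10.3 needs a sentence.

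**4. The plan's own precision figure.** Section 10.2 gives a 95% half-width of 0.9 SD with 10 per group. The formula is critical value × √(2/10), and √(2/10) = 0.447.
- Normal: 1.96 × 0.447 = 0.877 SD.
- t, 18 df: 2.101 × 0.447 = 0.940 SD.

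Both round to 0.9, so the figure reproduces.

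**5. What a baseline would change.** The documents give no pre/post correlation r for either measure, so r from 0.3 to 0.8 is assumed. With equal pre and post SDs and a common linear slope, a baseline difference of d SD carries about r × d into an unadjusted post contrast. With a baseline covariate, and group baseline means close to each other, the half-width is about t(17 df) × √(2/10) × √(1 − r²) = 2.110 × 0.447 × √(1 − r²).

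| r (assumed) | carried into post contrast at d = 0.5 SD | 95% half-width with baseline |
|---|---|---|
| 0.3 | 0.15 SD | 0.90 SD |
| 0.5 | 0.25 SD | 0.82 SD |
| 0.7 | 0.35 SD | 0.67 SD |
| 0.8 | 0.40 SD | 0.57 SD |

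The comparison without a baseline is 0.94 SD.

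**6. Is d = 0.5 SD plausible?** Two random samples of 10 would differ at baseline with a standard error of 0.447 SD. The chance of a difference beyond 0.5 SD is 2 × (1 − Φ(0.5/0.447)) = 26%. Consecutive enrolment can add a systematic difference of unknown size.

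**The case against.** The strongest case on the other side is that post-only timing looks deliberate. Section 3.1 separates pre/post change in function, symptoms and quality of life from a post-only report of readiness for discharge by patients and caregivers. Table 5 puts both scales in the readiness and self-management block. This stands for the Care Transitions Measure, which is rightly post-only. A sponsor could also call caregiver preparedness part of readiness. It does not supply a prior value for non-randomised groups, and both forms can be answered before PACT.

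Three stronger readings are tempting, and the documents do not support them:

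- *Table 5 contradicts Section 5.1.* A reader might infer this from 5.1's promise of an identical baseline battery in both groups. That battery is limited to quality of life, symptom and functional measures, so there is no contradiction.
- *The stated primary model certainly fails for these measures.* The sub-heading may exclude them, so this holds on only one of the two readings.
- *The full chance range of baseline differences, ±0.88 SD (1.96 × 0.447), is bias in the result.* If the groups were chance samples, it would be sampling variation that the post-only interval already reflects. Bias comes from a systematic difference between earlier and later enrolees, and only about r × d of it reaches the post contrast.

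Further points stand. Period and selection effects touch every outcome in this design, and a baseline on two scales would not remove them. The demographic sensitivity analysis may capture some prior difference, but only so far as demographics track activation or preparedness. At r = 0.3 the gain in precision is small. The study disclaims power and formal testing, and Section 3.5 is redacted, so the formal status of these measures cannot be seen.

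**Conclusion.** The point holds as a gap in the schedule and in the analysis text that is cheap to close. It does not invalidate the study. For patient activation and caregiver preparedness, the plan yields a post-only contrast between consecutive groups, with no means of adjusting for prior levels and no estimate of change.

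The size is conditional. A prior difference of 0.5 SD would shift the contrast by about 0.15 to 0.40 SD for r between 0.3 and 0.8. The gain in half-width runs from negligible (0.94 to 0.90 SD at r = 0.3) to material (0.94 to 0.67 SD at r = 0.7). These figures rest on 10 analysable patients, or caregivers, per group, on the assumed r, and on equal SDs. The size of any systematic difference between the groups cannot be derived from the documents.

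**What to change.** In Table 5, mark both measures at the cycle 1 baseline and state that they are completed before the first PACT contact. A mark alone is not enough: the baseline window runs to 3 days after infusion initiation, while PACT starts on day 1 or 2. Apply the same day limit to controls, so that both groups are measured at a comparable time.

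In Section 10.3, name both measures among the outcomes analysed by the baseline-adjusted ANCOVA. State that the Care Transitions Measure is compared between groups without baseline adjustment. When reporting, note that adjustment reduces measured imbalance but leaves period effects and unmeasured differences in place.

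The cost is 13 patient items and 8 scored caregiver items at a contact already planned: a few minutes and a slight increase in burden.

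A further administration at the cycle 3 baseline is optional. The last scheduled value falls at about days 37-44 (infusion ending about day 37, plus up to 7 days), before or early in the home nurse calls on days 38-60. The planned cycle 3 questionnaire is for patients, so caregivers might need an added contact.
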